Trichuriasis is a parasitic disease caused by nematodes belonging to the group of soil-transmitted helminths (STH). It is estimated that around 400 million people harbour infections with *Trichuris trichiura* globally [1]. As it is the case for all STH infections, trichuriasis is mainly endemic in developing countries in tropical and subtropical regions, with highest burden among rural communities due to its link to poor sanitation [2].

Infection with *T. trichiura* occurs when ingesting embryonated eggs via soil-contaminated hands, drinking water or food. Having reached the small intestine, the eggs hatch realising the larvae. The larvae migrate directly into the cecum where they develop into adult worms and begin to oviposit. Eggs are excreted into the soil via the faeces, thereby closing the life cycle [3].

Acute symptoms of trichuriasis are generally mild or not apparent in infected individuals living in endemic areas [2, 4]. The main disease burden results from chronic infection and repeated re-infection, in which symptoms related to the location of adult worms such as abdominal pain may develop. Long-term infection compromises the life of people by hampering their physical and mental development, limiting their work performance and overall quality of life [4].

The recent World Health Organization (WHO) road map for neglected tropical diseases targets STH infections for near to global elimination as a public health problem by 2030 [5]. One important intervention to achieve this is preventive chemotherapy (PC) [5-7]. The aim of PC is to reduce worm burden and hence morbidity in endemic populations by regular large-scale administration of anthelminthic drugs to high-risk groups, *e.g.* preschool-aged and school-aged children [8, 9]. The frequency of such mass drug administration (MDA) depends on the local infection prevalence [8, 9]. At present, the benzimidazoles albendazole and mebendazole are the most widely used drugs for PC campaigns against STH infections [7, 10]. These drugs are characterized by high cure rates (CRs) against infections with *Ascaris lumbricoides* (>95%) and moderate CRs against hookworm infections (80%). However, at single oral doses suitable for MDA, these drugs have demonstrated unsatisfactory efficacy against *T. trichiura* infections [11, 12].

Therapies combining two or more drugs are widely advocated in different therapeutic areas. The advantages of multifactorial pharmacological treatment include the increase and broadening of efficacy over drugs being administered in monotherapy and the protection against the selection of drug resistance, and hence, a prolongation of the life-span of effective and available drugs [13-15]. In 2017, ivermectin in combination with albendazole for treatment of STH was added to the Essential Medicines List (EML), paving the way to further evaluate the efficacy of this combination treatment among children and communities in a range of epidemiological settings [16]. While evidence on the superiority of ivermectin-albendazole combination compared to single standard treatments against STH infections, including trichuriasis, in school-aged children, adolescents and adults is growing, efficacy of this combination has not yet been assessed in the high-risk population of preschool-aged children (PSAC)

[17, 18]. An important reason for this knowledge gap is that oral ivermectin is not licensed for treatment of individuals with a bodyweight of <15 kg (corresponding to children aged less than ~5 years). Nevertheless, within the past two decades the safety data on individuals weighing <15 kg increased substantially and there are many efforts to develop oral ivermectin for small children suffering from scabies [19].

Another major drawback in the applicability of oral ivermectin in PSAC is the lack of a formulation suitable for administration to small children who may not be able to swallow the standard ivermectin tablets. Tablets offered to young children in a crushed or suspended form are prone to imprecise dosing and come with reduced palatability, and thereby a higher chance to be expelled out of the mouth by the child. Currently, several new orodispersible tablet (ODT) formulations, which are suitable for the hot and humid tropical conditions found in most countries in need, are being developed.

There is a need to explore whether these new ivermectin ODT formulations could reveal a benefit in the treatment of STH infections in PSAC. Based on the data of a study investigating the optimal ivermectin dose in PSAC infected with T. trichiura in Côte d'Ivoire, it was suggested to administer higher doses than the standard dose in adults (200 µg/kg) to reach equivalent bioavailability [20, 21]. In this trial, we aim to determine the optimal dose of ivermectin, as a newly developed orodispersible tablet formulation, in combination with albendazole in terms of efficacy and safety in treating T. trichiura infections in PSAC on Pemba Island, Tanzania. Furthermore, we re-assess pharmacokinetic (PK) parameters of ivermectin ODTs compared to standard ivermectin tablets. The PK characterization of a drug is essential to understand the response of the human body to a drug and vice versa, especially in populations that physiologically differ from healthy adults. Physiological characteristics like mal- or undernutrition due to intestinal worms, such as T. trichiura, can potentially affect the PK of a drug [22, 23]. Age, sex, bodyweight but also the presence of certain enzymes in different populations are important contributors to the PK profile of a drug. Our study will be the first one to provide PK information on a new ivermectin ODT in PSAC with trichuriasis and thus guide optimal drug dosing in this high-risk population. Finally, acceptability (including palatability) of a drug is important to ensure compliance and effectiveness of treatment. Therefore, this study includes the assessment of drug acceptability applying visual analogue scales (VAS).

3. Trial objective and purpose

We designed a dose-ranging trial to identify the most appropriate dose of ivermectin in terms of efficacy and safety in treating trichuriasis in individuals aged 2-5 years on Pemba Island, Tanzania. This study will provide further insights on the pharmacokinetics and acceptability of a novel orodispersible formulation as compared to the standard tablets. Our data will pave the way for possible phase 3 follow-up studies and support the development of ivermectin for children aged <6 years and its implementation in control programs.

The **primary objective** is to determine the ivermectin dose-response relationship in terms of CR in *T. trichiura*-infected children aged 2-5 years, assessed at 14-21 days post-treatment by quadruplicate Kato-Katz microscopy.

The **secondary objectives** of the trial are:

- a) to determine the *T. trichiura* egg reduction rates (ERRs) of treatments;
- b) to determine the CRs and ERRs of treatments against *Ascaris lumbricoides* and hookworm co-infection;
- c) to evaluate the safety and tolerability of the treatments.
- d) to characterize population PK of ivermectin ODTs compared to standard tablets in *T. trichiura* infected individuals;
- e) to assess the acceptability of the treatments.

The **exploratory objective** of this trial is to assess the diagnostic performance of FECPAKG2.

4. Methodology

4.1 Primary and secondary endpoint

Primary endpoint: *T. trichiura* infection status of participants at 14-21 days post-treatment assessed by quadruplicate Kato-Katz.

Secondary endpoints:

- *T. trichiura* infection intensity of participants at 14-21 days post-treatment assessed by quadruplicate Kato-Katz;
- *A. lumbricoides* and hookworm infection status and intensity of co-infected participants at 14-21 days post-treatment assessed by quadruplicate Kato-Katz;
- Tolerability of treatments (adverse events (AEs) at three and 24 hours and 14-21 days post-treatment;
- Population PK parameters of ivermectin ODTs and standard tablets in *T. trichiura* infected PSAC;
- Acceptability (including palatability).

Exploratory endpoints: Diagnostic characteristics of FECPAKG2 (infection intensity, sensitivity, and specificity) compared to Kato-Katz.

4.2 Trial design

A parallel randomised controlled dose-ranging trial will be conducted with six treatment arms (Figure 1). The study includes a baseline screening (day -60 to -1) and clinical baseline assessment (day 0) before treatment and post-treatment assessments for, pharmacokinetics (day 0 to 1), safety (day 0, 1 and 14 to 21) and efficacy (day 14 to 21). It is designed as a dose-ranging trial with 210 participants aged 2-5 years randomised to ivermectin ODT placebo and albendazole (400 mg), ascending doses of ivermectin ODT ($100 \mu g/kg$, $200 \mu g/kg$, $300 \mu g/kg$, or $400 \mu g/kg$, respectively) and albendazole (400

mg), or the standard ivermectin tablets (200 μg/kg) and albendazole (400 mg), with an allocation ratio of 1:1:1:1:1:1 (*i.e.*, 35:35:35:35:35:35:35). This trial will be conducted in communities in the Wete district on Pemba Island with high endemicity as identified in previous studies on *T. trichiura*.

[figure not shown]

Figure 1. Trial design and timeline.

4.3 Procedures

4.3.1 Diagnosis

At baseline, all participants will be asked to provide two stool samples. From each stool specimen, duplicate Kato-Katz thick smears (41.7 mg each) [24] will be prepared and read under a microscope for eggs of *T. trichiura*, *A. lumbricoides* and hookworm by experienced technicians. Eggs per gram (EPG) will be assessed by adding up the egg counts from the quadruplicate Kato-Katz thick smears and multiplying this number by a factor of six. For quality control of *T. trichiura* and *A. lumbricoides* egg counts, 10% of slides will be re-read by another laboratory technician. Results are considered correct if the following tolerance margin is not exceeded: (i) No difference in presence/absence of *T. trichiura* and *A. lumbricoides* (ii) egg counts are +/-10 eggs for counts ≤100 eggs or +/-20% for counts >100 eggs (for each species separately). In case discrepancies above the tolerance margin are noted in one or more slides, the respective slides are re-read by the local technicians. The new results are discussed, so that in case of discordant results, slides can be re-evaluated to reach consensus. All microscopically analysed quadruplicate Kato-Katz thick smears will be destroyed after passing the quality control. The same diagnostic approach will be applied at 14-21 days after treatment (see section 4.3.8).

4.3.2 FECPAKG2

Research on new diagnostic tools is necessary, since the currently recommended Kato-Katz technique has a low sensitivity for low STH infections and slides with hookworm eggs cannot be re-examined [25-27]. Once moving towards transmission control and STH elimination, an increased sensitivity of the diagnostic method of choice is crucial [28]. Preferably, a diagnostic method that could potentially replace Kato-Katz would be sensitive, specific, fast, simple, cost-effective and re-analysis could be conducted at any time.

The aim of this exploratory objective within this trial is the comparison of infection intensity, sensitivity, and specificity of the Kato-Katz technique with the novel diagnostic tool FECPAKG2 (Techion). FECPAKG2 is an online, remote location, parasite diagnostic system used in veterinary medicine [29]. An image of the Kato-Katz slide is captured, stored offline on a computer, and can be uploaded onto a cloud once connected to the internet. Subsequently, specialists around the world can analyse the image at any time. Techion's image capture devices are robust, reliable, versatile and cost effective [30]. Baseline quadruplicate Kato-Katz thick smears will be used to take images by FECPAKG2 after the slides have been read by technicians under the microscope.

4.3.3 Clinical examination

A clinical examination of the study participants assessing general health, anthropometric parameters including height and weight as well as temperature using a non-contact infrared forehead thermometer (Braun No touch – NTF3000; Braun, Kronberg, Germany) will precede the treatment. Each participant will be asked to provide a finger-prick blood sample to measure haemoglobin (Hb) levels, which will be detected using a HemoCue analyzer (Hb 301 system, Angelholm, Sweden). In case of abnormal values, results from baseline clinical examination may be reported back to parents/caregivers during the trial period. Parents/caregivers of trial participants will be asked about existing clinical symptoms before drug administration using a standardised questionnaire.

4.3.4 Treatment of participants

All eligible participants will be treated with the respective treatment regimen according to their treatment arm assigned by randomisation at day 0. Ivermectin tablets (ODT and standard tablets) will be obtained from Liconsa, and an individual number of tablets according to bodyweight and dose will be administered. Albendazole will be the product of GSK (Zentel®) and a single tablet of 400 mg will be administered. Placebo tablets will be purchased from Zentiva Pharma GmbH, Germany.

The tablets will be handed out from four drug containers (placebo, ivermectin ODT, ivermectin standard tablets, and albendazole). According to the randomisation list, each person will receive either:

- (i) Placebo (number corresponding to 200 µg per kg bodyweight) plus a single tablet of albendazole
- (ii) 100 μg ivermectin ODT per kg bodyweight plus a single tablet of albendazole
- (iii) 200 µg ivermectin ODT per kg bodyweight plus a single tablet of albendazole

- (iv) 300 µg ivermectin ODT per kg bodyweight plus a single tablet of albendazole
- (v) 400 µg ivermectin ODT per kg bodyweight plus a single tablet of albendazole
- (vi) 200 µg ivermectin standard tablets per kg bodyweight plus a single tablet of albendazole

All drugs will be administered in the presence of the Principal Investigator (PI) and/or Co-PI, and ingestion confirmed. This will be recorded with the time and date of dosing. Participants will be asked to limit the use of any drugs other than those prescribed by the study medical team for the duration of the study as described in section 5.5. After ingestion of the medication, the participants will be observed for three hours to ensure retention of the drug. Vomiting within one hour post-dosing will require redosing. The participants will not be allowed more than one repeated dose. No re-administration will be needed for participants vomiting after one hour. The PI or the Co-PIs are responsible for drug accountability at the study site. Maintaining drug accountability includes careful and systematic study drug storage, handling, dispensing, and documentation of administration. Prior to administration, drugs will be stored at room temperature and protected from light and exposure to moisture in a secure area with limited access at the study site.

To avoid interference of potential on-going control programs against helminthiases with the infection status of the trial participants, communication with local stakeholders will be established to ascertain that trial participants will not undergo MDA treatment. Missed-out rounds of planned MDA against STH infections will be substituted with a free single-dose treatment (albendazole 400 mg) against STH infection after the follow-up assessment, offered by the study team to all community members not participating in the trial in communities screened.

4.3.5 Pharmacokinetic analysis

The PK and exposure-response correlation study will be performed in 24 participants in the two treatment arms receiving either ivermectin ODT 200 μ g/kg or ivermectin standard tablets 200 μ g/kg (12 per selected treatment arm). Since PK population parameters of ivermectin are available, a sparse sampling approach can be applied to describe the PK profile [31]. Within a sparse sampling approach, instead of describing the PK profile for each participant separately, samples are allocated to different time points and/or individuals within the same treatment. Statistical inferences are performed to characterize the population-based PK profile of a specific treatment arm. This approach allows for a reduced number of samplings per treatment arm and renders a PK characterization well tolerable. To this end, a small drop of blood from the fingertip will be taken for a maximum of 5 finger pricks per participant. The exact time points are 1h, 2h, 4h, 6h, and 24h, covering the relevant time span identified previously [31, 32]. Capillary blood (~60 μ l) will be collected by puncture with a finger prick. Two micro-samples (duplicates) will be taken with one finger prick. Each time, the drop of blood (60 μ l) will be directly transferred on dried-blood spot cards. The dried cards will be transported to Swiss TPH and stored at room temperature until analysis (< 2 months post-treatment). The quantification of the study

drugs will be performed using the validated liquid chromatography tandem mass spectrometry (LC-MS/MS) method as described elsewhere [32]. Drug concentrations will be calculated by interpolation from a calibration curve with a lower limit of quantification of 1-5 ng/ml. 7% of the sample duplicates will be analysed for quality control, and the measured concentrations will be used to determine between-run and overall precision and accuracy of the analysis.

4.3.6 Assessment of acceptability

To better understand the acceptability of ivermectin ODT compared to standard ivermectin tablets in PSAC, the palatability of each formulation (ODT and standard tablets crushed and swallowed with water) will be rated by children aged 4-5 years using a 100 mm VAS incorporating a 5-point pictorial hedonic scale (Figure 2) [33]. This rating will take place within 5 minutes after receiving the treatment. Additionally, participants will complete a short questionnaire directly after treatment administration and the interviewers will observe the participants during medication administration and record any discomfort or difficulties in taking the medication.

[figure not shown]

Figure 2. 100 mm hedonic visual analogue scale [33].

4.3.7 Safety assessment

Participants will be monitored at the site (*i.e.* health centre) for three hours after treatment administration to observe any possible acute AEs (continuous observation) and reassessment will be done at 24 hours post-treatment (follow-up visit). Additionally, interviews will be conducted with parents/caregivers to determine the emergence of clinical symptoms such as headache, abdominal pain, itching, nausea, vomiting and diarrhoea directly before treatment within the scope of baseline assessment. At three and 24 hours and 14-21 days after treatment parents/caregivers will again be interviewed for the assessment of AEs. Symptoms arising within three hours after treatment and the follow-up time points will be monitored by parents/caregivers or local healthcare workers who will report incidences to the study team. Any symptoms will be recorded in the designated case report form (CRF) and immediate action will be undertaken if indicated.

4.3.8 Efficacy assessment

The efficacy of the treatment will be determined at 14-21 days post-treatment by collecting another two stool samples, which will be microscopically examined for *T. trichiura*, *A. lumbricoides* and hookworm eggs using quadruplicate Kato-Katz thick smears (two slides per sample). Quality control will be performed as described for the initial diagnosis (see section 4.3.1). All microscopically analysed quadruplicate Kato-Katz thick smears will be destroyed after passing the quality control.

Participants will be considered cured for an infection if no corresponding eggs are found in the followup stool samples. At the end of the study, all participants remaining positive for *T. trichiura* or any coinfection will be treated with the currently best recommended treatment.

4.4 Measure to minimise bias

Study participants eligible for treatment will be randomly assigned to one of the six treatment arms using a computer-generated stratified randomisation code. The random allocation sequence with a block size of 6 stratified by two levels of age category (24-47 months and 48-71 months) and two levels of baseline *T. trichiura* infection intensity (light: 1-999 EPG, and moderate or heavy: ≥1000 EPG) will be provided by a statistician. Allocation concealment will be warranted using opaque, sealed envelopes containing the randomisation lists. All treatment arms will be single-blinded (*i.e.* study participants will be blinded) using appearance and texture matching placebos. Only the study pharmacist administering the treatment will be aware of treatment allocation; all trial team members assessing the outcomes will remain uninformed. In the case of accidental unblinding or necessary code breaks, the sponsor will be immediately notified (within 24 hours) and data will be analysed as set forth in section 8.3.

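### Allocation concealment in 4.4 is weaker than it need be: one fixed block size equal to the number of arms, and envelopes that hold lists instead of single allocations

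*Combined protocol and SAP*

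**What the plan says.** Section 4.2 sets out the arms and the ratio: "A parallel randomised controlled dose-ranging trial will be conducted with six treatment arms", "with an allocation ratio of 1:1:1:1:1:1". Section 4.4 gives one block size: "The random allocation sequence with a block size of 6 stratified by two levels of age category". The second stratification factor is baseline infection intensity, also at two levels, so there are four strata.

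On concealment, 4.4 says: "Allocation concealment will be warranted using opaque, sealed envelopes containing the randomisation lists". It mentions neither one envelope per child nor sequential numbering. On who knows the allocation, it says: "Only the study pharmacist administering the treatment will be aware of treatment allocation". Outcome assessors are to remain uninformed.

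Section 4.3.4 says: "All drugs will be administered in the presence of the Principal Investigator (PI) and/or Co-PI". The same section has tablets taken from four separate containers, in a number that depends on dose and bodyweight. The placebo count follows the 200 µg/kg dose. Section 4.3.6 describes the standard tablets as crushed and taken with water.

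**The concern.** Two features weaken concealment.

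- **The envelopes.** If an envelope holds a list, opening it for one child shows the arm of every later child on that list.
- **The blocks.** With six arms at equal ratio and blocks of six, each arm occurs exactly once per block. Someone who knows the earlier allocations in a block can narrow down the rest, and the last one follows by elimination.

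The second route needs someone other than the pharmacist to learn the earlier allocations. The PI or Co-PI may partly do so at dosing, from the tablet numbers, the container used and the crushed standard tablets. The block size is no secret from them: it is in the protocol, which the investigators are to discuss in detail before the start (section 7). Section 9.3 gives the Co-PIs responsibility for recruitment and for monitoring enrolment.

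What is at stake is which child enters which arm. Table 1 places medical history, clinical examination and haemoglobin at 0h, just before randomisation and treatment. Foreknowledge at that point could affect a judgement about systemic illness or the order in which children come forward. Uninformed slide readers protect the measurement of the endpoint, but not entry into the arms.

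**Working it through.** **Inputs from the documents.** Six arms at equal ratio (4.2); block size 6 and four strata (4.4); 35 per arm and 210 in total (8.2). The total reproduces: 6 × 35 = 210, which is 210/6 = 35 blocks. (The expanded ratio in 4.2 prints seven entries of 35, which would give 245; only six fit.)

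**Step 1: upper bound without sight of a list.** The observer is assumed to know each child's stratum and every earlier arm. At position k of a block, 6 − k + 1 arms remain, equally likely, so the best guess is right with probability 1/(6 − k + 1):

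| Position | 1 | 2 | 3 | 4 | 5 | 6 |
|---|---|---|---|---|---|---|
| Correct | 16.7% | 20% | 25% | 33.3% | 50% | 100% |

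Mean = (1/6 + 1/5 + 1/4 + 1/3 + 1/2 + 1)/6 = 49/120 = 40.8%, against 1/6 = 16.7% by chance. Over 210 children that is 0.408 × 210 ≈ 86 correct guesses, against 35 by chance.

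**Step 2: certain allocations.** One per completed block, so 35 of 210 (16.7%) if all blocks are complete. Four strata can each end in an unfinished block of 0 to 5 children. These remainders must add up to a multiple of six and cannot exceed 4 × 5 = 20, so they total 0, 6, 12 or 18. Completed blocks therefore number 35, 34, 33 or 32.

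**Step 3: placebo and ODT 200 µg/kg indistinguishable.** Positions 1 to 5 are unchanged. At position 6 the remaining arm is one of the four identifiable arms with probability 4/6 (certain), or one of the look-alike pair with probability 2/6 (a coin toss): 4/6 + (2/6)(1/2) = 5/6. Mean = (1/6 + 1/5 + 1/4 + 1/3 + 1/2 + 5/6)/6 = 38.1%. The exact arm is then certain in 35 × 4/6 ≈ 23 children.

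**Step 4: strata ignored.** An observer who always names the arm least used so far, pooled over four strata assumed equally frequent, is right 29.5% of the time (simulation, 2,000 runs of 210).

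**Step 5: sight of a list.** All remaining allocations on that list are known.

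**Step 6: after varying the block size.** The sizes are assumptions of this review. The observer is again the worst case: sees every arm, knows the stratum and knows the set of sizes, but not which size applies to each block (simulation, 4,000 runs of 54 children in a stratum).

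| Block sizes | Correct guesses | Certain |
|---|---|---|
| 6 only (plan) | 40.8% | 16.7% |
| 6 and 12 | 37.2% | 5.2% |
| 6, 12 and 18 | 34.8% | 2.5% |

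With 6 and 12, about 0.052 × 210 ≈ 11 allocations stay certain instead of 35.

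**The case against.** The strongest reply has four parts.

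- **Presence is not knowledge.** Section 4.3.4 has the PI or Co-PI attend dosing and has ingestion confirmed. It does not say that they see the list or the container. Reading the dose from a tablet count also needs the child's weight, and 4.4 provides placebos matched in appearance and texture. This stands: exact identification of all six arms is an assumption, so 41% is an upper bound. Partial inference remains possible, because the standard tablets are crushed and the tablet count changes with dose.
- **The list-holder is not the gatekeeper.** On the text, the pharmacist handles allocation. The study physician examines the child before treatment, and 9.3 lists the two roles separately. A reader might infer that everyone present at dosing can read ahead on the list; no section says so.
- **Little discretion is left.** Consent and Kato-Katz results precede day 0, Table 1 puts randomisation after the clinical examination, and the named examples of systemic illness are measured limits. This stands in large part. Residual clinical judgement and the order of children remain.
- **The wording may be loose.** The lists may in fact be individual slips. The text does not say so; if slips are intended, one sentence closes that part.

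It can also be said that varying the blocks gains little in average guessing (41% to 37%). That is fair: its main effect is on certain allocations, and the envelopes bring the larger gain.

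**Conclusion.** The point holds as a cheap improvement to concealment. As written, 4.4 lets the holder of an opened list see all later allocations on it, and it makes the last slot of each complete block deducible by anyone who has followed the earlier ones. Without sight of a list, the size is at most 41% correct guesses against 17% by chance, with 32 to 35 of 210 certain. It is 38% if placebo and ODT 200 µg/kg look alike, and about 30% if strata are ignored. These figures rest on an observer who identifies every arm, except for that pair in the 38% case.

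Three stronger readings are not supported:

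- **That the block size was public during enrolment.** The documents show only that it is stated in the protocol, which the investigators discuss.
- **That varying blocks would leave no allocation certain.** About 5% would stay certain with sizes 6 and 12 if the set of sizes became known.
- **That the cure rates are biased.** Guessing success is not bias. No effect on the cure rates has been quantified, and the room for selection is confined to day 0.

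Sections 4.3.4 and 4.4 still need to agree on who can see or infer the allocation.

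**What to change.** In 4.4:

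1. Use one sequentially numbered, opaque, sealed envelope per child within each of the four strata, opened only after the day 0 eligibility check is signed. If this is already intended, say so.
2. Use permuted blocks of randomly varying size in multiples of six (for example 6 and 12), with the sizes held only by the statistician and not stated in the protocol.
3. Reconcile 4.4 with 4.3.4 on what the PI or Co-PI can see of the allocation at dosing.

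The cost is a regenerated list and 210 envelopes. The possible imbalance in a small stratum grows slightly: two arms can differ by at most one child in an unfinished block of 6, and by at most two in a block of 12. The sample size stays at 210.
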